Annex 3 bis

Annex 3 ter

Annex 4

Annex 5

Annex 6

Annex 7

Annex 8

Annex 9

Annex 10

Annex 11

Annex 12

Rationale of the Study and Risk/Benefit analysis

Keratoconus is a naturally-occurring ocular condition characterized by progressive thinning and steepening of the central cornea, resulting in corneal optical irregularities with increasing myopia, irregular astigmatism, corneal opacity and consequential loss of visual acuity. Clinical onset of the disease begins in the second decade of life and has significant social impact due to its progression towards vision loss; indeed, keratoconus still represents the primary cause of corneal transplantation in young adults globally.

Riboflavin/UV-A corneal cross-linking is a procedure used to biomechanically stabilize the weak cornea in keratoconus and to slow down or halt the clinical progression of this disease. The procedure has been performed in Europe since 2003, thereafter the procedure has been adopted in eastern countries and United States. The standard corneal cross-linking protocol, also known as *Dresden protocol*, consists in removing the epithelium and administering a riboflavin ophthalmic solution onto the corneal stroma for 30 minutes; afterwards the cornea is irradiated by a UV-A light device using 3mW/cm^2 power density for 30 minutes, with a total delivered energy of 5.4 J/cm^2 . According to the systematic review and meta-analysis studies, the standard cross-linking protocol is effective (where efficacy is indicated as stabilization or flattening of the maximum simulated keratometry value, K_{\max}) in almost 70% of treated cases, with a failure rate ranging from 8% to 33% one year after surgery. However, epithelial removal is the predisposing factor to the most frequent and major complications of the standard protocol, which include ocular pain, corneal haze, transient corneal edema in virtually all cases, and some severe adverse events, such as corneal infections, corneal melting, and corneal scarring, which may cause vision loss. For this reason, any improvement, which can increase the efficacy and minimize the risks of the gold standard surgical technique is highly desirable. Several transepithelial treatment protocols have been developed in order to minimize risks, nevertheless their clinical efficacy in comparison with the standard protocol still remains object of debate.

Theranostics is an emerging therapeutic paradigm that enables monitoring of image-guided therapy in clinic through the use of a theranostic module that makes use of real-time non-invasive molecular analysis of the tissue being treated to achieve optimal treatment outcomes in the management of disease.

This is a clinical study consisting of a study arm to assess the performance of the theranostic software module (Research Use Only) of a CE marked (CE1936) UV-A medical device, C4V CHROMO4VIS™, in order to validate its use for image-guided corneal cross-linking treatment of keratoconus and corneal ectasia. The study hypothesis is that theranostic-guided riboflavin/UV-A corneal cross-linking with the C4V CHROMO4VIS™ system is safe and can estimate treatment efficacy during operation, regardless of treatment protocol, i.e., either with or without epithelial

removal. The software module is able to measure the concentration of riboflavin into the cornea during treatment and to provide the surgeon with an objective assessment of treatment efficacy. The scope of this study is to validate the theranostic imaging biomarker score by assessing the change of corneal topography K_{max} value at 1-year postoperatively. The 1-year follow-up is long enough to provide scientific evidence of the safety and efficacy of the theranostic UV-A medical device in question. A pre-operative examination will ensure that every interested and willing participant fulfils the inclusion criteria of this study. Post-operative examinations will be carried out after 1 week, 1 month, 3 months, 6 months and 12 months.

The present study can start treatment of subjects only after an Independent Ethical Committee written approval; it is governed by three guiding principles: safety, ethical conduct, and efficiency. Subject safety guides study design by minimizing the number of participants exposed to serious adverse events.

Abbreviations

AE	Adverse Event
CDVA	Corrected Distance Visual Acuity
C4V CHROMO4VIS™	Theranostic UV-A medical device
C4V	Theranostic UV-A medical device acronym
CFR	Code of Federal Regulation
CRF	Case Report Form
CRO	Contract Research Organization
CTA	Clinical Trial Authorization
CV	Curriculum Vitae
CXL	Corneal cross-linking
D	Diopter
EpiOFF	Epithelium off
EpiON	Epithelium on or transepithelial
GCP	Good Clinical Practice
GDPR	General Data Protection Regulation
GMP	Good Manufacturing Practice
ICH	International Council for Harmonization
IEC	Independent Ethical Committee

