Numerical variables will be summarized as mean and standard deviation (SD) and as median and interquartile range (IQR). Categorical variables will be represented as frequencies and proportions. For numerical variables, paired Student t-test or Wilcoxon signed-rank test will be used to compare the distributions preoperatively and 12-months postoperatively. Bonferroni correction will be

applied to analysis of exploratory outcome measures of stratification groups. For all reported AEs, the data shall be presented with events listed in order of decreasing frequency.

Sites of Investigation

- Azienda Ospedaliera Universitaria Careggi, Università di Firenze
- Azienda Ospedaliera Universitaria Policlinico G. Martino, Università di Messina
- Azienda Ospedaliera Universitaria Mater Domini, Università Magna Graecia di Catanzaro

Coordinator Site of Investigation

- Azienda Ospedaliera Universitaria Mater Domini, Università Magna Graecia di Catanzaro

List of principal investigators

[name], ophthalmologist (UniFI)

[name], ophthalmologist (UniME)

[name], ophthalmologist (UniCZ)

Declaration of the Sponsor on the sources and types of financial, material and other support

The Sponsor has provided the clinical investigators and Site of Investigations with the Protocol (including Case Report Forms), the investigator's brochure, confidentiality, personal data safety and sponsor agreements, and any other documentation, which is necessary to complete the Study.

[figure not shown]
The Sponsor has verified in local audit that each clinical center has a designated clinical area and equipment as well as that the investigators are qualified and experienced to perform the present Study.

The Sponsor loans, free-of-charge, the medical devices and the equipment required to perform treatment to the Investigators/Institutions for the entire duration of the trial. The free of charge supply of these materials does not influence the scientific, technical and procedural autonomy of the Investigators and Study staff. The medical devices used in this Study will be stored and handled according to the applicable Laws. The equipment will be handled with care and used exclusively in the clinical trial. The Sponsor will train the investigators on how to use these devices. The Sponsor undertakes the liability insurance required for each subject enrolled in the Study.

Regulatory aspects and Funding Sources

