In this study, patients with progressive keratoconus receives a single dose of the ophthalmic solution RitSight™ (CE0477) delivered into the cornea manually for at least 15 minutes and treated by using the C4V CHROMO4VIS™ system with the theranostic software module while they are observed and tested for a period of 12 months after treatment to assess correlation between the theranostic imaging biomarker and the K_{max} flattening.

Follow-up for each participant is twelve months after treatment. The interval is long enough to observe treatment efficacy as well as any effect or complication induced by the innovative corneal cross-linking procedure performed by using the theranostic UV-A medical device in a participant.

Study Participants

The inclusion criteria are: diagnosis of progressive keratoconus. Participants with 18-40 years old are eligible, all genders.

According to the most recent scientific literature⁹, the criterion to determine progression of keratoconus is based on providing at least one of the following types of evidence:

- at least two Placido disk corneal topography measurements showing at least +1.00 D steepening of the K_{max} value in the last year or longer interval period.
- at least two central corneal thickness (CCT) measurements showing at least -10 µm change in in the last year or longer interval period.

⁹ Ferdi A, et al. Keratoconus Natural Progression: A Systematic Review and Meta-analysis of 11 529 Eyes. Ophthalmology 2019;126:935-945

The exclusion criteria are: corneal apex steeper than 63 D, corneal thickness thinner than 400 µm; corneal scarring; descemetocèle; history of herpetic keratitis; concomitant eye diseases; inflammatory eye diseases; glaucoma; cataract; nistagmus; pregnancy; breast feeding.

The study does not accept healthy volunteers.

If both eyes of a participant are eligible, the eye with lower CDVA will be chosen as the study eye.

Study Arm

One study arm receiving either corneal cross-linking treatment after epithelial debridement (“Theranostic Epi-OFF CXL”) or transepithelial corneal cross-linking treatment (“Theranostic Epi-ON CXL”). Only one eye of each participant is designated as the study eye.

Discontinuation of contact lens wear

Participants must discontinue the use of contact lenses from seven days before baseline visit to 3 months follow-up; thereafter, they must discontinue the use of contact lenses at least seven days before the remaining follow-up visits at day-180 and day-360.

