The Principal Investigator of Site of Investigation will be responsible for telephone or fax reporting of any SAE to the IEC. Site will notify the IEC by telephone or fax transmission of any unexpected, fatal, or life-threatening experience (expedited report) associated with the use of the study Treatment as soon as possible but no later than 7 calendar days after the initial receipt of the information. Initial notification will be followed by a written report within 15 calendar days. For unexpected events associated with the use of the study Treatment, Sponsor/CRO will notify the IEC as soon as possible, but no later than 15 days of the initial receipt of information. The principal investigator is responsible for informing the Ethical Committee. Copies of SAE correspondence with the principal investigator or investigators, governing authorities, ethics committees, and the sponsor must be submitted to Sponsor/CRO for filing.

Adverse Event Monitoring

A participant experiencing any AE or SAE will receive treatment and follow-up evaluations by the principal investigator of the Site of Investigation or will be referred to another appropriate physician for treatment and follow-up. All AEs, whether serious or non-serious, should be followed to resolution or until the AE is determined by the investigator not to be clinically significant.

List of adverse events reported in the specialized literature after CXL treatment

Summary of adverse events on total 9607 cases treated by CXL procedures (ref. bibliography)				
N	Type of adverse event	Intensity of adverse event	Cases (n.)	Incidence (%)
1	Bacterial keratitis	Severe	59	0.61%
2	Herpetic keratitis		5	0.05%
3	Corneal burn		1	0.01%
4	Corneal scarring		51	0.53%
5	CDVA loss (>2 ETDRS lines)		13	0.13%

6	Persistent corneal haze	Moderate	12	0.12%
7	Corneal infiltrates		54	0.56%
8	Epithelial ingrowth under LASIK flap		1	0.01%
9	Eyelid eczema	Mild	1	0.01%
10	Transient eye pain		18	0.19%
11	Transient ocular itching		1	0.01%
12	Transient visual fogging		16	0.17%
13	Dry eye		6	0.06%
14	Conjunctival hyperemia		10	0.10%
15	Transient corneal haze		499	5.19%
16	Transient corneal edema		74	0.77%

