The table above shows the adverse events reported in studies of eyes treated both by Epi-Off and Epi-On corneal cross-linking procedures. In these studies, the majority of AEs generally developed in the short-term. The percentage of AEs that resolved by 3 months study visit was 98%. The most common AEs (i.e., $\geq 10\%$) were corneal epithelium defect, corneal opacity, corneal edema/striae, eye pain, and punctate keratitis. Most of these events represented sequelae following corneal epithelial debridement. Indeed, the Epi-Off corneal cross-linking procedure involves removal of the corneal epithelial layer, which is expected to result in reduction of vision due to the injury to the epithelium. The reduction in visual function and other adverse reactions generally resolve with the healing of the epithelium by the first week after treatment, though visual recovery to baseline values may take up to 3 months after treatment.

Treatment strategy for adverse events

Any adverse event is monitored in order to respond promptly and adequately to each of them. Since all participants will administer antibiotic/disinfectant eye drops and lubricant eye drops immediately after dosing and treatment, the majority of adverse event is managed preventively according to the standard of care after corneal cross-linking. The use of anti-inflammatory eye drops may be required in the case of moderate or severe ocular surface inflammation in a participant. The use of paracetamol pills may be used in the event of unacceptable headache in a participant.

[figure not shown]
Statistical Considerations and Data Analysis

Stratification, Allocation and Enrolment

Eligible participants will be stratified with allocation ratio 1:1 into either theranostic-guided CXL treatment protocol using a computer-generated stratification plan with blocks. Two different blocks are created, which include eyes with K_{max} steeper or flatter than 54.0 D to stratify patients with comparable baseline K_{max} values in either theranostic-guided CXL treatment protocol.

This is a multi-center clinical trial. The stratification code is given to each local site of investigation by the central monitoring site of the Sponsor after the participant has been considered eligible to the study and has signed the informed consent. The enrolment is competitive. The period for enrollment includes the four months after study protocol approval by the IEC of the local site of investigation.

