Synopsis on disposition of participants

Sample size

By expecting a response rate of 50% of cases that will reach the threshold of -1.05 D of the K_{max} value, a sample size of 42 patients achieves 91% power to detect a difference of 0,25 between the area under the ROC curve (AUC) under the null hypothesis of 0,60 and an AUC under the alternative hypothesis of 0,85 using a two-sided z-test at a significance level of 0,05000. The data are continuous responses. Considering a $\leq 20\%$ drop-out rate (determined from systematic literature review on controlled and open clinical studies on standard and epithelium-on CXL procedures), a number of 50 participants (25 per treatment protocol) is allowed to be enrolled in the study.

Details on the methodology and process used to define the sample size of this clinical trial are described in Appendix 1 – Methodology for sample size calculation.

Statistical methodology

Descriptive statistics will be used to summarize the data: numerical variables will be summarized as mean and standard deviation or median and interquartile range, respectively, according to the distribution of the data; categorical variables will be represented as frequencies and proportions. Student's t-test or Wilcoxon test will be applied to compare continuous variables, while Fisher's exact test or Chi-Squared test will be used to analyze categorical variables. Bonferroni correction is applied to analysis of exploratory outcome measures of stratification groups. For all reported AEs, the data can be presented with events listed in order of decreasing frequency.

The optimal cut-off values in predicting the propensity of CXL treatment to flatten the Kmax value at 12-months was determined based upon the results of preclinical studies (data not disclosed to investigators to avoiding methodological study bias) and can be optimized with the Youden index. The accuracy and precision (95% CI) of the combined use of the theranostic imaging biomarkers to predict CXL treatment outcome will be determined by calculating the proportion of correctly classified eyes and the positive predictive value (PPV) respectively. The miss rate, which is the probability that a true positive is missed by the theranostic methodology, will be determined by calculating the false negative rate (FNR).

Statistical significance will be set at 0.05. All the analysis will be performed using the statistical software R (latest version available).

Population to be analysed

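### The hypothesis that the procedure is safe under either protocol cannot be supported for rare severe events by 50 treated eyes, and no interval is planned for any event rate

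*Combined protocol and SAP*

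**What the plan says.** The section on rationale and risk/benefit puts safety first in the hypothesis: "The study hypothesis is that theranostic-guided riboflavin/UV-A corneal cross-linking with the C4V CHROMO4VIS™ system is safe and can estimate treatment efficacy during operation". The same sentence extends this to both the epithelium-off and the transepithelial treatment. The next lines say: "The 1-year follow-up is long enough to provide scientific evidence of the safety and efficacy of the theranostic UV-A medical device in question".

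On numbers, the Sample size section states that "a number of 50 participants (25 per treatment protocol) is allowed to be enrolled in the study". The Study Arm section adds "Only one eye of each participant is designated as the study eye", and the allocation is 1:1. The only justification of size is the power of a test on the area under the ROC curve.

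On adverse events, the Data Analysis part of the Synopsis says: "For all reported AEs, the data shall be presented with events listed in order of decreasing frequency". Statistical methodology repeats this in weaker form (can rather than shall). Categorical variables in general are to be shown as counts and proportions. Confidence intervals are mentioned only alongside the predictive-performance measures. No acceptable event rate or safety margin is set.

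The prespecified safety outcome is the 12-month change in endothelial cell density (ECD). Corrected acuity (CDVA) and slit-lamp examination are named safety assessments, and central corneal thickness (CCT) is listed as a further safety outcome.

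The document gives several background rates for severe events:
- below 0.2% for the standard procedure (device chapter, Adverse Events);
- 0.2% for Epi-OFF and none for Epi-ON (Risk Assessment and Management);
- below 0.8% cumulatively (riboflavin chapter, Side effects);
- the counts in the table titled "Summary of adverse events on total 9607 cases treated by CXL procedures".

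**The concern.** A hypothesis that a procedure is safe under either protocol needs data that could contradict it. For infection, scarring or loss of acuity, that depends on how many eyes are treated. One year may be long enough for such events to appear, but 50 eyes may be too few for even one to appear, whatever the follow-up.

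The plan neither sets a rate to be excluded nor plans an interval that would show what was excluded. A short or empty list of severe events could then be read as support for the hypothesis when it mostly reflects the small denominator. The investigation is declared to be part of the clinical evaluation for conformity assessment (Regulatory aspects and Funding Sources), so the wording of a safety statement matters.

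**Working it through.** **1. The plan's own figure.** The stated power is 91% with 42 patients, AUC 0.60 against 0.85, two-sided 0.05, 50% responders (21 and 21). The Hanley-McNeil variance is [A(1−A) + 20(Q1−A²) + 20(Q2−A²)]/(21×21), with Q1 = A/(2−A) and Q2 = 2A²/(1+A).
- A = 0.60: variance 3.411/441, SE 0.0880.
- A = 0.85: variance 1.632/441, SE 0.0608.
- Power = Φ[(0.25 − 1.96×0.0880)/0.0608] = Φ(1.276) = 89.9%.

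This reproduces the stated figure to within about a point. The size is therefore explained by the AUC test, and no safety precision enters it.

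**2. Upper limit when no severe event is seen.** The exact two-sided 95% (Clopper-Pearson) limit for 0 of n is 1 − 0.025^(1/n).
- n = 50: 1 − 0.025^(1/50) = 7.1% (one-sided, with 0.05: 5.8%).
- n = 25, one protocol: 1 − 0.025^(1/25) = 13.7% (one-sided 11.3%).
- n = 42, if only the evaluable number were used: 8.4%.
- For comparison, 1 event in 50 gives an interval of 0.05% to 10.6%.

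**3. Background rate from the literature table.** Rows 1 to 5 (bacterial keratitis, herpetic keratitis, corneal burn, corneal scarring, CDVA loss) give (59 + 5 + 1 + 51 + 13)/9607 = 129/9607 = 1.34%. This makes two assumptions: that the Severe label, printed once against row 1, covers all five rows, and that each event is a different eye. If some eyes had more than one event, the rate per eye is lower.

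**4. Comparison.** The chance of no event in 50 eyes is (1−p)^50.

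| Background rate p | 7.1% limit as a multiple of p | 13.7% limit as a multiple of p | Chance of no event in 50 | Eyes needed, with no event, for the two-sided limit to reach p |
|---|---|---|---|---|
| 0.2% | 36 | 69 | 90% | 1,843 |
| 0.8% | 8.9 | 17 | 67% | 460 |
| 1.34% | 5.3 | 10 | 51% | 273 |

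The last column is ln(0.025)/ln(1−p), rounded up. It shows the scale of the gap and is not a proposed sample size.

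**5. If the true rate were higher than the background.**
- From 1.34%: the chance of no event in 50 is 26% if the rate is doubled and 13% if tripled.
- From 0.2%: it is 61% at five times the rate (1.0%) and 36% at ten times (2.0%).

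How much a clean result would say therefore depends strongly on which background figure is meant, and the document does not say which.

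**The case against.** The strongest reply is that the plan does not set out to prove safety. The Study objective and the Aim concern biomarker validation. The Reports section lists what the Final Report must conclude on: the biomarkers, Kmax, ECD, and exploratory acuity and refraction. A conclusion on adverse-event rates, or that the procedure is safe, is not on that list. A reader might infer from the Rationale that the trial is bound to declare the procedure safe, but the documents do not support that. Safety stands as a hypothesis and as a claim to provide evidence, not as a required conclusion. The follow-up sentence is about duration and is not itself wrong; the weakness lies in the hypothesis sentence.

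A reader might also infer that the trial says nothing about safety. That is not so either. ECD, CDVA, CCT and slit-lamp findings are planned, paired tests are specified for numerical variables, and 50 eyes can inform all of these. The gap is confined to rare severe events.

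A third tempting reading is that a clean list would be likely even if the device were clearly worse than the literature. From the 1.34% baseline that fails: 26% and 13% are not likely outcomes. Against the 0.2% figure it has more force (61% at five times the rate).

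It can also be said that counts, proportions and a known denominator let anyone compute a limit, that any 50-eye study shares this restriction, and that the document rests rare-event safety partly on CE marking and published experience. All of this is fair and keeps the point modest. It does not remove the mismatch: safety under either protocol is in the hypothesis, and nothing in the analysis states what these eyes could exclude.

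**Conclusion.** The point holds for rare severe events and is of modest importance. With no severe event, the trial could exclude only rates above 7.1% overall and 13.7% in one protocol. Those limits are about 5 to 36 times, and about 10 to 69 times, the non-zero rates the document quotes. The direction does not depend on which rate is chosen or on a one- or two-sided limit; the one-sided 5.8% is still 4.3 times the highest background figure.

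The calculation assumes that all 50 are treated, one eye each, with independent events. The 1.34% figure rests on the two table assumptions stated above; if either fails in the direction of a lower rate, the multiple grows. The background figures also name different sets of events, so they are not interchangeable. The result does not affect the primary analysis, and it gives no reason to enlarge the trial for its primary aim.

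**What to change.** 1. In the Rationale, restrict the safety part of the hypothesis, and any later safety conclusion, to the measured safety outcomes (ECD, CDVA, CCT, slit lamp) and to the absence of an unexpected safety signal in N treated eyes.
2. In Data Analysis and Statistical methodology, add one table of severe and sight-affecting events with exact Clopper-Pearson 95% limits, overall and by cross-linking protocol, using all treated eyes as the denominator. Define in advance which events count.
3. State beforehand the highest rate the trial can exclude: 7.1% overall and 13.7% per protocol if no event is seen.
4. Reconcile the background severe-event rates in the device chapter, the riboflavin chapter, the literature table and Risk Assessment and Management, and name the one used as comparator, with its event definition.

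The cost is some wording and one table, with no extra participants or visits. The downside is a more modest safety claim.
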